**Figure 1. Cycle 1 Dosing Ramp-Up Schematic**

IV = intravenous; SC = subcutaneous

### Screening

Screening procedures must be performed within 21 days prior to first dose of study drug administration. Longer intervals require discussion with the Medical Monitor. Once screening procedures are complete and eligibility is confirmed, subjects will be enrolled.

### Study Treatment

All subjects will receive venetoclax (daily for 28 days), in combination with azacitidine or decitabine, beginning on Cycle 1 Day 1. Depending on investigator's choice, subjects will receive either azacitidine for 7 days beginning on Day 1 of each 28-day cycle or decitabine for 5 days beginning on Day 1 of each 28-day cycle, as per institutional practice. The subject is to remain on their assigned therapy for the duration of the study. All subjects will receive a maximum of 6 cycles of venetoclax during the study period. After the study period ends, subjects may continue receiving AML-directed therapy including commercially-acquired standard-of-care treatments for venetoclax and azacitidine or decitabine.

### Cycle Length – (28 Days)

- Venetoclax orally daily: 100 mg on Cycle 1 Day 1, 200 mg on Cycle 1 Day 2, and 400 mg on Cycle 1 Days 3 – 28; 400 mg daily for each 28-day cycle thereafter.
- Azacitidine 75 mg/m^2 subcutaneous (SC) or intravenous (IV) for 7 days beginning on Day 1 of each cycle, as per institutional practice.
- Decitabine 20 mg/m^2 intravenous (IV) for 5 days beginning on Day 1 of each cycle, as per institutional practice.

Subjects with progressive disease for whom the treating physician feels are still deriving clinical benefit can be continued on treatment after discussion with the medical monitor or until no longer achieving

clinical benefit per investigator assessment, unacceptable toxicity, withdrawal of consent, or the subject meets other protocol criteria for discontinuation (whichever occurs first). All subjects will have a Final Visit performed when treatment is discontinued or when the end of the 6th cycle has been achieved unless the subject has withdrawn consent to participate in the study. Baseline laboratory assessments will be obtained at Cycle 1 Day 1 prior to first dose of study drug administration. Disease assessments by modified IWG criteria (Operations Manual, Section 3.16) will be performed at the timepoints described in Section 3.14 of the Operations Manual.

## 4.2 Discussion of Study Design

---

### Choice of Control Group

Not applicable.

### Appropriateness of Measurements

Standard statistical, clinical, and laboratory procedures will be utilized in this study. All effectiveness measurements in this study are standard for assessing disease activity in subjects with AML. All clinical and laboratory procedures in this study are standard and generally accepted.

### Suitability of Subject Population

Subjects who have histological confirmation of AML, who are treatment naïve, greater than or equal to 12 years of age, and who are not eligible to receive intensive chemotherapy due to co-morbidity or other factors will be selected to participate in this study.

Preliminary studies have demonstrated that venetoclax in combination with azacitidine or decitabine can induce responses for patients with AML and be dosed safely. Additionally, these clinical studies indicate that the combination may be more efficacious than either agent alone (Study M14-358). Therefore, given the prognosis, current limited effective options, safety of venetoclax and HMAs to date, and the preclinical signals of efficacy, the subject population is suitable.

### Selection of Doses in the Study

The currently approved venetoclax dose is 400 mg in combination with either azacitidine or decitabine and 600 mg in combination with low-dose cytarabine. This study will adhere to the US label in terms of dosing and, thus, the target venetoclax dose is 400 mg in combination with either azacitidine or decitabine. The regimen is designed to ramp up the dose of venetoclax rapidly with azacitidine or decitabine thereby optimizing the opportunity for achieving a response and enabling close subject monitoring. The dosing regimen will also enable interruptions and extensions at dose levels if rapid tumor lysis is observed. To date, this strategy has been effective at minimizing the risk of clinical TLS with a rate across the AML program at < 1%.

## 5 STUDY ACTIVITIES

### 5.1 Eligibility Criteria

---

Subjects must meet all of the following criteria in order to be included in the study. Anything other than a positive response to the questions below will result in exclusion from study participation.

#### Consent

- 1. Subjects or their legally authorized representative must voluntarily **sign and date an informed consent**, approved by an independent ethics committee (IEC)/institutional review board (IRB), prior to the initiation of any screening or study-specific procedures.

#### Demographic and Laboratory Assessments

- 2. Subjects must be at least 12 years old.
- 3. Subjects must have a projected life expectancy of at least 12 weeks.
- 4. **Laboratory values** meeting the following criteria within the screening period prior to the first dose of study drug:
  - Serum alanine aminotransferase (ALT)  $\leq 3 \times$  upper limit of normal (ULN)\*
  - Serum aspartate aminotransferase (AST)  $\leq 3 \times$  ULN\*
  - Bilirubin  $\leq 1.5 \times$  ULN\*

*\* Unless considered to be due to leukemic organ involvement or if a patient has confirmed Gilbert's disease.*

- Creatinine clearance  $\geq 30$  mL/min; calculated by the Cockcroft Gault formula or measured by 24-hour urine collection

$$\text{eCCr} = \frac{(140 - \text{Age}) \times (\text{Weight in kg}) \times [0.85 \text{ if Female}]}{72 \times \text{Serum Creatinine (mg/dL)}}$$

Or, if serum creatinine is in  $\mu\text{mol/L}$ :

$$\text{eCCr} = \frac{(140 - \text{Age}) \times (\text{Weight in kg}) \times [1.23 \text{ if Male, 1.04 if Female}]}{\text{Serum Creatinine (\mu\text{mol/L})}}$$

- White blood cell (WBC) count  $< 25 \times 10^9/\text{L}$  (hydroxyurea is permitted to meet this criterion)
- 5. Subjects must have an Eastern Cooperative Oncology Group (ECOG) Performance status of 0 to 3.
- 6. Are willing or able to comply with procedures required in this Protocol.

## Disease Activity

- ✓ 7. Subject must have confirmation of AML by WHO criteria and, as determined by the investigator, must be ineligible for treatment with a standard cytarabine and anthracycline induction regimen and deemed by the investigator as an appropriate candidate for outpatient ramp-up of venetoclax.
- ✓ 8. Subject meets the following disease activity criteria:
  - Subject must not have received any prior treatment for AML with the exception of hydroxyurea.
  - Subject has no evidence of spontaneous TLS at Screening.
  - Subject can have progressed from myelodysplastic syndrome (MDS) or be considered to have secondary AML and could have been treated with growth factors or other agents with the exception of HMAs.

## Subject History

- ✓ 9. Subject has no history of the following conditions:
  - Acute promyelocytic leukemia.
  - Known active central nervous system (CNS) involvement with AML.
  - Positive for HIV (HIV testing is not required).
  - Positive for hepatitis B or C infection, with the exception of those with an undetectable viral load within 3 months (Hepatitis B or C testing is not required). Subjects with serologic evidence of prior vaccination to hepatitis B virus [i.e., HBs Ag–, and anti-HBs+] may participate.
  - Cardiovascular disability status of New York Heart Association Class > 2. Class 2 is defined as cardiac disease in which patients are comfortable at rest but ordinary physical activity results in fatigue, palpitations, dyspnea, or anginal pain.
  - Chronic respiratory disease that requires continuous oxygen, or significant history of renal, neurologic, psychiatric, endocrinologic, metabolic, immunologic, hepatic, cardiovascular disease, or any other medical condition that in the opinion of the investigator would adversely affect his/her participating in this study.
  - Malabsorption syndrome or other condition that precludes enteral route of administration.
- ✓ 10. No history of **other malignancies** within 2 years prior to study entry, with the exception of:
  - Adequately treated in situ carcinoma of the cervix uteri or carcinoma in situ of breast.
  - Basal cell carcinoma of the skin or localized squamous cell carcinoma of the skin.
  - Previous malignancy confined and surgically resected (or treated with other modalities) with curative intent.
- ✓ 11. No history of clinically significant (per investigator's judgment) **drug or alcohol abuse** within the last 6 months.

- 12. No conditions that could **interfere with drug absorption** including but not limited to short bowel syndrome.
- 13. No history of clinically significant medical conditions or any other reason that the investigator determines would **interfere with the subject's participation** in this study or would make the subject an unsuitable candidate to receive study drug.
- 14. No history of an **allergic reaction** or significant sensitivity to constituents of the study drug (and its excipients) and/or other products in the same class.
- 15. No clinically relevant or **significant electrocardiogram (ECG) abnormalities**, including ECG with QT interval corrected for heart rate (QTc) using Fridericia's formula (QTcF) > 450 msec (males) or > 470 msec (females) at Screening.

### Contraception

- 16. Female subjects must be either postmenopausal defined per one of the following criteria:
  - Age > 55 years with no menses for 12 or more months without an alternative medical cause.
  - Age ≤ 55 years with no menses for 12 or more months without an alternative medical cause AND a follicle-stimulating hormone (FSH) level > 40 IU/L.
  - Permanently surgically sterile (bilateral oophorectomy, bilateral salpingectomy, or hysterectomy).

OR,

- 17. Female subjects of childbearing potential must practice at least 1 protocol-specified **method of birth control** that is effective from Cycle 1 Day 1 through at least 90 days after the last dose of study drug.
- 18. For all female subjects of childbearing potential, negative results should be obtained for pregnancy tests performed:
  - At Screening, with a serum sample obtained within 14 days prior to the first dose of study drug administration, and
  - Prior to dosing obtained on Cycle 1 Day 1, with urine sample if it has been > 7 days since obtaining serum pregnancy test results.
- 19. Female who is not **pregnant, breastfeeding, or considering becoming pregnant** during the study, from Screening through at least 90 days after the last dose of study drug.
- 20. Male who is not considering **fathering a child or donating sperm** during the study from Cycle 1 Day 1 through at least 90 days after the last dose of study drug. For subjects receiving azacitidine, this period is 6 months following the last dose of azacitidine.
- 21. **If male**, and subject is **sexually active with female partner(s) of childbearing potential**, he must agree, from Cycle 1 Day 1 through at least 90 days after the last dose of study drug, to practice the protocol-specified contraception. For subjects receiving azacitidine, this period is 6 months following the last dose of azacitidine.

## Concomitant Medications

- ✓ 22. Subject has not received treatment with the following:
  - CAR-T cell therapy
  - Prior therapy or experimental therapies for AML
- ✓ 23. Subject has not consumed grapefruit, grapefruit products, Seville oranges (including marmalade containing Seville oranges) or star fruit within 3 days prior to the initiation of study treatment.
- ✓ 24. Subject must not have received **any investigational drug** within the 30 days prior to the first dose of study drug or must not be currently enrolled in another clinical study.
- ✓ 25. Subject must not have systemically used known strong or moderate CYP3A inducers within 7 days prior to the initiation of study treatment.
- ✓ 26. Subject must not have received **any live vaccine** within 4 weeks prior to the first dose of study drug, or expected need of live vaccination during study participation including at least 4 weeks after the last dose of study drug.

## 5.2 Contraception Recommendations

---

### Contraception Requirements for Females

Subjects must follow the following contraceptive guidelines as specified:

- Females, Non-Childbearing Potential  
Females do not need to use birth control during or following study drug treatment if considered of non-childbearing potential due to meeting any of the following criteria:
  - Postmenopausal, age > 55 years with no menses for 12 or more months without an alternative medical cause
  - Postmenopausal, age ≤ 55 years with no menses for 12 or more months without an alternative medical cause AND an FSH level > 40 IU/L
  - Permanently surgically sterile (bilateral oophorectomy, bilateral salpingectomy, or hysterectomy)
  - Females who have not experienced menarche (at least one menstrual period)
- Females, of Childbearing Potential
  - Females of childbearing potential must give consent to abide by contraception requirements
  - Females of childbearing potential must avoid pregnancy while taking study drug(s) and for at least 90 days after the last dose of study drug
  - Females must commit to one of the following methods of birth control:
    - Combined (estrogen and progestogen containing) hormonal birth control (oral, intravaginal, transdermal, injectable) associated with inhibition of ovulation initiated at least 30 days prior to Cycle 1 Day 1

- Progestogen-only hormonal birth control (oral, injectable, implantable) associated with inhibition of ovulation initiated at least 30 days prior to Cycle 1 Day 1
- Bilateral tubal occlusion/ligation (can be via hysteroscopy, provided a hysterosalpingogram confirms success of the procedure)
- Intrauterine device (IUD)
- Double-barrier method (contraceptive sponge, diaphragm or cervical cap with spermicide AND a condom)
- Intrauterine hormone-releasing system (IUS)
- Vasectomized partner (provided the partner has received medical confirmation of the surgical success of the vasectomy and is the sole sexual partner of the trial subject)
- Practice true abstinence, defined as: Refraining from heterosexual intercourse when this is in line with the usual and preferred lifestyle of the subject (periodic abstinence [e.g., calendar, ovulation, symptothermal, post-ovulation methods] and withdrawal are not acceptable)

#### Contraception Requirements for Males

Male subjects who are sexually active with a female partner of childbearing potential, must agree **to use condoms, even if the male subject has undergone a successful vasectomy**, from Cycle 1 Day 1 through at least 90 days after the last dose of study drug. For subjects receiving azacitidine, this period is 6 months following the last dose of azacitidine.

- His female partner(s) must also use at least 1 of the following methods of birth control:
  - Combined (estrogen and progestogen containing) hormonal birth control (oral, intravaginal, transdermal, injectable) associated with inhibition of ovulation initiated at least 30 days prior to Cycle 1 Day 1
  - Progestogen-only hormonal birth control (oral, injectable, implantable) associated with inhibition of ovulation initiated at least 1 month prior to Cycle 1 Day 1
  - Bilateral tubal occlusion/ligation (can be via hysteroscopy, provided a hysterosalpingogram confirms success of the procedure)
  - Intrauterine device (IUD)
  - Contraceptive sponge, diaphragm or cervical cap with spermicide
  - Intrauterine hormone-releasing system (IUS)

## 5.3 Prohibited Medications and Therapy

---

In addition to the medications and therapy listed in the eligibility criteria (Section 5.1, concomitant medications), the following is not allowed during the study (refer to the Operations Manual, [Appendix J](#)):

- Grapefruit, grapefruit products, Seville oranges, or star fruits are not allowed during the study
- Strong or moderate CYP3A inducers are prohibited 7 days prior to the first dose of study drug
- Strong CYP3A inducers are prohibited through the end of the study

Subjects must be consented for the study before discontinuing any prohibited medications for the purpose of meeting study eligibility.

A sample list of excluded and cautionary medications, with additional guidance noted, is provided in [Appendix D](#).

## 5.4 Prior and Concomitant Therapy

---

If a subject reports taking any over-the-counter or prescription medications, vitamins, and/or herbal supplements, or if administration of any medication becomes necessary, beginning with the screening visit through the end of the study, the name of the medication, dosage information including dose, route and frequency, date(s) of administration including start and end dates, and reason for use must be recorded. Although cautionary, use of strong or moderate CYP3A inhibitors or moderate inducers, or P-gp substrates or inhibitors are allowed if no appropriate therapeutic alternative exists (refer to the Operations Manual, Section 3.3). Concomitant use of a moderate CYP3A inducer should be avoided. Alternative treatments with less CYP3A induction or inhibition should be considered. Concomitant use of a P-gp substrate should be avoided. Alternative treatments should be considered. If use of P-gp substrate is unavoidable, P-gp substrate should be separately dosed at least 6 hours before venetoclax. Herbal supplements known to inhibit or induce CYP3A or P-glycoprotein (P-gp) should be excluded and use of other supplements should be discouraged. Transfusion of blood and blood products, antibiotics, anti-fungals, anti-emetics, granulocyte-colony stimulating factor (G-CSF), and other standard supportive care medications are permitted as needed, per institutional practices. Anti-uric acid agents (such as hydroxyurea or allopurinol) or leukapheresis are also permitted per institutional guidelines and to decrease WBC counts to  $< 25 \times 10^9/L$  at the time of study entry or during the study, as needed.

Filgrastim may be administered, per clinical practice.

Venetoclax dose modifications for co-administration with strong or moderate CYP3A inhibitors and P-gp inhibitors during Cycle 1 and after ramp-up are noted below and in [Table 1](#). Two to three days post the removal of the strong or moderate CYP3A inhibitor or P-gp inhibitor, venetoclax treatment will be given at the target dose of 400 mg without the need to ramp-up.

- For subjects who are on a strong CYP3A inhibitor, at the time of initiation, the dose of venetoclax will be reduced ([Table 1](#)) for the duration of treatment with the strong CYP3A inhibitor.

- For subjects who are on posaconazole, at the time of initiation, the dose of venetoclax will be reduced ([Table 1](#)) for the duration of treatment with posaconazole.
- For subjects who are on a moderate CYP3A inhibitor (such as ciprofloxacin, fluconazole or isavuconazole) or a P-gp inhibitor (such as amiodarone or captopril), the venetoclax dose will be reduced by 50% ([Table 1](#)) for the duration of treatment with the moderate CYP3A inhibitor or P-gp inhibitor.

**Table 1. Dose Modification for Venetoclax When Co-administered with P-gp Inhibitors or Moderate or Strong CYP3A Inhibitors**

Venetoclax Dose (mg) a	Venetoclax Dose if Co-Administered with 1 or more Strong CYP3A Inhibitor	Venetoclax Dose if Co-Administered with posaconazole	Venetoclax Dose if Co-Administered with 1 or more Moderate CYP3A Inhibitor or P-gp Inhibitor
100 mg (Cycle 1 Day 1 only)	10 mg	10 mg	50 mg
200 mg (Cycle 1 Day 2 only)	20 mg	20 mg	100 mg
400 mg (Cycle 1 Day 3)	50 mg	50 mg	200 mg
400 mg (Cycle 1 Day 4 and daily thereafter)	100 mg	70 mg	200 mg
400 mg (Target Dose after Ramp-up)	100 mg	70 mg	200 mg

CYP3A = Cytochrome P450 3A; P-gp = P glycoprotein

a. If a subject requires co-administration of venetoclax with both a strong and a moderate CYP3A inhibitor or a P-gp inhibitor, venetoclax dose modification recommended for strong CYP3A inhibitors should be followed.

Any questions regarding concomitant or prior therapy should be raised to the AbbVie emergency contact. Information regarding potential drug interactions with venetoclax (ABT-199) can be located in the Venetoclax Investigator's Brochure. A sample list of excluded and cautionary medications is provided in [Appendix D](#).

If a CYP3A inhibitor or P-gp inhibitor is discontinued, resume the venetoclax target dose 2 to 3 days after discontinuation of the inhibitor.

Subjects must be able to safely discontinue any prohibited medications 4 weeks prior to first dose of study drug administration. Subjects must be consented for the study prior to discontinuing any prohibited medications for the purpose of meeting study eligibility.

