Study M14-387 evaluated the safety and efficacy of venetoclax in combination with low-dose cytarabine in patients with previously untreated AML who were ineligible for intensive chemotherapy due to comorbidities or age. Venetoclax was initiated at 50 or 100 mg daily and dose escalated over 4 – 5 days to reach 600 mg. In subsequent 28-day cycles, venetoclax was administered at 600 mg on all days. Low-dose cytarabine (20 mg/m^2 daily) was administered SC on Days 1 – 10 of each cycle. At the beginning of the study, concomitant strong and moderate cytochrome P450 3A isoform subfamily (CYP3A) inhibitor use was prohibited; however, as additional safety and pharmacokinetic data became available, their use was allowed with appropriate venetoclax dose adjustments. The most common adverse events of Grade  $\geq 3$  across all subjects were febrile neutropenia (43%), thrombocytopenia (38%), neutropenia (27%), and anemia (27%). Laboratory evidence of Grade 3 TLS was observed in 2 subjects; both subjects achieved the target dose of venetoclax. Forty seven percent of subjects received moderate (40%) or strong (7%) CYP3A inhibitors for at least 7 days (predominantly azole antifungals); no relevant differences in serious adverse event rates were observed. Median time to first response was 1.4 months, and 54% and 46% of subjects achieved CR/CRI and CR/complete remission with partial hematologic recovery (CRh), respectively. The rates of CR/CRI for subjects with secondary and de novo AML were 35% and 71%, respectively; median duration of response for those with secondary and de novo AML was 8.1 and 11.6 months, respectively.

Supported by these results, 2 randomized trials (Studies M15-656 and M16-043) have been initiated evaluating venetoclax in combination with the common frontline treatments of azacitidine or low-dose cytarabine in subjects with treatment-naïve AML who are ineligible for intensive chemotherapy.

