- If any clinically significant laboratory changes are observed within the first 24 hours after initiation of dosing or after a dose escalation, see [Appendix F](#) for management guidelines. Refer to table in [Appendix E](#) for definitions of laboratory and clinical TLS.
- If subjects develop TLS and the treatment is withheld, they should be admitted and managed as inpatient until the ramp-up is complete and TLS labs have normalized.

Subjects with reduced renal function ( $\text{CLcr} < 80 \text{ mL/min}$ , Cockcroft-Gault formula) require more intensive prophylaxis and monitoring to reduce the risk of TLS when initiating treatment with venetoclax. For subjects with a higher risk for TLS and lower creatinine clearance, additional measures with more intensive lab monitoring and intervention should be implemented ([Appendix F](#)).

If a subject meets criteria for clinically significant laboratory or clinical TLS please follow institutional guidelines or recommendations in [Appendix G](#); no additional venetoclax dose should be administered until resolution.

For continued dosing of venetoclax, monitor for evidence of TLS during study treatment, and manage abnormalities of serum creatinine, and electrolytes promptly. After resolution of electrolyte imbalances ([Appendix F](#)), venetoclax may be continued at the original dose after discussion between the investigator and the AbbVie TA MD.

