### Management of Other Toxicities

If other events occur that are related to venetoclax, azacitidine, or decitabine, the investigator, in consultation with the AbbVie medical monitor, may interrupt or reduce the dose of venetoclax and/or azacitidine or decitabine, as appropriate. Grade 3 or greater nonhematologic toxicity (e.g., nausea, vomiting, and diarrhea when additional supportive care fails or neurotoxicity, AST, ALT, or bilirubin increased), that is related to venetoclax, azacitidine, or decitabine will require interruption and possible discontinuation of dosing. Venetoclax, azacitidine, or decitabine may be reintroduced, but only at a reduced dose, (in consultation with the AbbVie medical monitor) if the toxicity returns to ≤ Grade 1 or to baseline if Grade 2 at study entry.

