#### Dose Modifications for Venetoclax

See [Appendix G](#) for dose modifications for toxicities related to venetoclax. Venetoclax dose modifications for possible drug-drug interactions are provided in the Section [5.4](#).

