## APPENDIX G. RECOMMENDED DOSE REDUCTIONS RELATED TO DRUG TOXICITIES IN AML

### Recommended Venetoclax Dose Modifications for Toxicities

Event	Occurrence	Action
Hematologic Toxicities		
Grade 4 neutropenia with or without fever or infection; or Grade 4 thrombocytopenia (see Warnings and Precautions in Management of Cytopenias, Section 6.2)	Occurrence prior to achieving remission	Transfuse blood products, administer prophylactic and treatment anti-infectives as clinically indicated. In most instances, venetoclax and azacitidine or decitabine cycles should not be interrupted due to cytopenias prior to achieving remission.
	First occurrence after achieving remission and lasting at least 7 days	Delay subsequent treatment cycle of venetoclax and azacitidine or decitabine and monitor blood counts. Administer granulocyte-colony stimulating factor (G-CSF) if clinically indicated for neutropenia. Once the toxicity has resolved to Grade 1 or 2, resume venetoclax therapy at the same dose in combination with azacitidine or decitabine or low-dose cytarabine.
	Subsequent occurrences in cycles after achieving remission and lasting 7 days or longer	Delay subsequent treatment cycle of venetoclax and azacitidine or decitabine and monitor blood counts. Administer G-CSF if clinically indicated for neutropenia. Once the toxicity has resolved to Grade 1 or 2, resume venetoclax therapy at the same dose and the duration reduced by 7 days for each subsequent cycle.

AML = acute myeloid leukemia; G-CSF = granulocyte-colony stimulating factor.

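### Section 5.4 returns venetoclax to 400 mg once an inhibitor is stopped, with no exception for a subject on a toxicity-reduced dose

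*Protocol*

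**What the plan says.** **The rule.** Protocol Section 5.4 reduces venetoclax while a strong or moderate CYP3A inhibitor or a P-gp inhibitor is in use (Table 1), in Cycle 1 and after ramp-up. It then says twice what happens when the inhibitor stops. Before Table 1, 2 to 3 days after removal, "venetoclax treatment will be given at the target dose of 400 mg without the need to ramp-up". After Table 1: "If a CYP3A inhibitor or P-gp inhibitor is discontinued, resume the venetoclax target dose 2 to 3 days after discontinuation of the inhibitor".

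**Toxicity reductions.** Under Management of Other Toxicities (Section 6.2), related nonhematologic toxicity of Grade 3 or greater requires interruption. Once it has settled, the drug "may be reintroduced, but only at a reduced dose", in consultation with the sponsor's medical monitor.

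**The link between the two.** Dose Modifications for Venetoclax (Section 6.2) sends the reader to Appendix G for toxicity, and adds: "Venetoclax dose modifications for possible drug-drug interactions are provided in the Section" 5.4. Appendix G, as it appears, covers hematologic toxicity only and leaves the mg dose alone; for repeat occurrences, for example, the site is to "resume venetoclax therapy at the same dose and the duration reduced by 7 days for each subsequent cycle".

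**Tumor lysis.** Section 4.2 says the regimen will "enable interruptions and extensions at dose levels if rapid tumor lysis is observed", and Section 2.2 says the same. If TLS develops and treatment is withheld, Section 6.2 says of these subjects that "they should be admitted and managed as inpatient until the ramp-up is complete and TLS labs have normalized".

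**The concern.** Stopping an inhibitor should remove only the reduction that was made because of the inhibitor. Section 5.4 instead names a fixed dose, 400 mg, whatever other reason the subject may have for being on less.

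The clear case is a subject whose venetoclax was restarted at a reduced dose after a related Grade 3 or greater nonhematologic toxicity. The reduction was the condition for restarting. If that subject later stops an azole, say, Section 5.4 calls for 400 mg within days, which could bring back the exposure that led to the toxicity.

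A second, less clear case is a subject kept at 100 or 200 mg in Cycle 1 because of tumor lysis. For that subject the words waiving ramp-up could be taken to waive the remaining steps.

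What is at stake is dosing safety in a study meant to show that outpatient initiation is safe. The remission rate, its confidence interval and the sample size are not touched.

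**Working it through.** The plan states no figure to reproduce. The check compares the dosing rules and then takes simple ratios.

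**1. What the target dose means.** Section 4.2 and the last row of Table 1 use the term for 400 mg, not for the subject's own dose before the inhibitor. Both sentences in Section 5.4 therefore mean 400 mg.

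**2. Toxicity-reduced subject.** At the time the inhibitor stops:

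| Source | Dose |
|---|---|
| Section 5.4, both sentences | 400 mg |
| Section 6.2, Management of Other Toxicities | a reduced dose, size not given |

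Let R be the reduced dose without an inhibitor. The ratio is 400/R. The values of R are assumptions:
- R = 100 mg: 400/100 = 4.0
- R = 200 mg: 400/200 = 2.0
- R = 300 mg: 400/300 = 1.33

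**3. Is there a precedence rule?** Dose Modifications for Venetoclax divides the subject matter but does not rank the two sections. The consultation with the medical monitor attaches to reintroduction, not to a later inhibitor stop. The discussion required under Adverse Events of Special Interest (Section 6.1) concerns further reductions. Operations Manual Section 3.3 adds no exception. Section 5.9 bars intentional deviations except for an immediate hazard, so a site in this position must depart from one instruction or the other.

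**4. Ramp-up.**
- Uninterrupted: an inhibitor stopped on Day 1 or later gives 400 mg on Day 1 + 2 = Day 3 at the earliest. Section 4.1 already schedules 400 mg from Day 3, so there is no conflict.
- Kept at a level because of tumor lysis, if the waiver is read to cover the remaining steps: against the same step without an inhibitor, 400/100 = 4.0 at step 1 and 400/200 = 2.0 at step 2. The nominal change is larger because it also lifts the interaction reduction. With a moderate inhibitor at step 1, 50 to 400 mg is 8 = 2 × 4; with a strong one, 10 to 400 mg is 40 = 10 × 4. Only the last factor could be put down to the rule.

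**5. Frequency.** The only usable figures are indirect.
- Section 4.2 puts clinical TLS across the AML program below 1%: fewer than 60 × 0.01 = 0.6 subjects.
- Section 2.1 reports of a related study with a low-dose cytarabine backbone: "Forty seven percent of subjects received moderate (40%) or strong (7%) CYP3A inhibitors for at least 7 days". If that held here, 60 × 0.47 = 28.2 subjects would use such an inhibitor. This counts users, not those who stop.
- Both, if independent: fewer than 0.6 × 0.47 = 0.28 subjects. This is still too high for the ramp-up case as far as clinical TLS goes, because the 2 to 3 day point must also fall inside an extended ramp-up. Laboratory TLS and P-gp inhibitor use are not counted.
- Restart after Grade 3 or greater toxicity: the documents give no rate.

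**The case against.** The best defense is one of scope. The Section 5.4 paragraph is about co-administration, so its last step ends the interaction reduction and nothing else. The toxicity text in Section 6.2 is operative in its own right, and a specific, restrictive rule would ordinarily prevail over a general one. A careful investigator would probably read it that way, and Section 5.4 sends questions about concomitant therapy to a sponsor contact. All of this lowers the risk. It does not supply a precedence rule: Section 5.4 is itself a positive dosing instruction, given twice, and nothing in it prompts the site to ask.

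The silence of Appendix G should carry little weight. The TLS text in Section 6.2 refers to recommendations there that do not appear in the table as read, so rows may have been lost. The point does not depend on it.

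A reader might also infer that Section 5.4 tells sites to skip ramp-up steps after tumor lysis. The documents do not support that:
- The second sentence speaks of resuming the target dose, which does not fit a subject who has never reached it.
- The waiver in the first sentence can be read as no repeat ramp-up.
- Section 6.2 requires TLS chemistry to be reviewed before the next dose, allows the dose to be withheld or reduced, bars dosing until TLS resolves, and calls for inpatient care until ramp-up is complete if treatment is withheld.
- Extension at a dose level without a hold appears only in the rationale text of Sections 2.2 and 4.2.

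What remains is an ambiguity, because the first sentence's paragraph does cover Cycle 1.

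Nor does the rule override a second inhibitor still in use. The Section 5.4 bullets and the Table 1 column headings keep that reduction in force.

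**Conclusion.** The point holds for the toxicity-reduced subject. Taken literally, Section 5.4 gives 400 mg where Section 6.2 allows only a reduced dose, and no text ranks the two. On assumed reduced doses of 100 to 300 mg, the excess is 4.0- to 1.3-fold. For a subject kept at a ramp-up level because of tumor lysis, the wording is unclear but largely governed by Section 6.2; the 4.0- and 2.0-fold ratios apply only on the less natural reading.

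Cases should be few, but that is a judgment: the documents give no rate for the toxicity case, and the 28 of 60 and fewer than 0.3 of 60 figures rest on rates carried over from other studies and, for the second, on independence. The point is minor. It concerns dosing safety and changes no endpoint, analysis or sample-size figure.

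**What to change.** At both sentences in Section 5.4, write: *Two to three days after the inhibitor is stopped, resume the dose that applies without that inhibitor (400 mg if ramp-up is complete and no toxicity reduction applies), subject to Table 1 for any other inhibitor still in use and to Section 6.2.*

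This protects a toxicity reduction and also settles the ramp-up ambiguity. It costs one qualifying clause in each of two places, with no added visits, tests or staff.
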